The superscripts associated with each outcome in the “How Answered” boxes in figure 2 refer to the following strategies for testing the hypotheses in Aims 1 and 2: (a) A survey called the Patient Activation Measure (PAM), (Appendix A-1) is completed by patient 1-2 weeks after their visit²²; (b) The “no show rate” is the inverse of Return Visit Adherence (RVA) rate;²³ (c) the Refill rate is “proportion of days covered” (PDC), a metric CMS utilizes in its plan ratings;²⁴ and (d) BP and HgB A1c are checked if they are repeated within 6 months; (e) The SEGUE Framework for evaluating and scoring communication behavior, as rated off of the audio recording by a research assistant utilizing a checklist (Appendix A-2)²⁵ and (f) Content Coding for Contextualization of Care, also called “4C”²⁶. Note: (b-d) are extracted from the CDW and SEGUE and 4C completed while accessing the medical record and listening to the audios. Finally, for all three arms, the members of the research team collecting the data and coding the audio are blinded as to study arm. There is no arm in which the patient is unaware a visit is audio recorded. Blinding the patient is not pertinent to achieving the aims of the study.

Figure 3, the flow diagram below, allocates patients in a parallel three arm randomized controlled trial (RCT) to most efficiently achieve the aims of the study (the calculations for the specific sample sizes are justified later in the protocol – and shown in Tables 4.1 and 4.2. on pp 24+25).

Figure 3: Flow diagram for parallel RCT

Random assignment to arms will be made using computer-generated sequences within the diabetes clinics (1:1 randomization to Arms 1 and 2 in blocks of 4) and primary care clinics (5:5:2 randomization to Arms 1, 2, and 3, in blocks of 24, with one partial block of 8 patients). Solid lines represent unconditional allocation of participants to Arms; dashed lines represent random sampling of participants to create efficient unbiased subsamples for key hypothesis tests. The rationale for the design, starting at the top of the figure and working down, is as follows:

- We start with two separate pools, diabetes and primary care clinics, because measurement of the effect of OAA vs control (Arm 1 vs Arm 2) on Hgb A1c is most efficiently accomplished

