just in the diabetes clinics where every patient has diabetes, many have an A1c>8, and A1c is re-checked at frequent intervals. Hence, analysis of an effect of OAA on diabetes control will occur only in the diabetes clinic population.

- All other measures to achieve Aim 1 will occur in analysis of data collected in both the diabetes and primary care clinics. Hence data on the effect of OAA on show-rates (visit adherence), medication refill rates, blood pressure control etc...will be pooled for patients randomized to Arms 1 and 2 in both the diabetes and primary care clinics.
- The PAM will be applied to the smallest possible subsample of Arms 1 and 2 to test hypothesis 1A (figure 2) with 80% power (Table 4.1, p 24) because it requires a phone call and takes about three minutes of RA and patient time. Subsamples will be drawn at random without replacement by computer. As shown in the Gantt chart (Table 2, p. 18), these calls will be spread out and administered 1-2 weeks post visit (Table 4.0, p 23). This is in contrast to measures of blood pressure, Hgb A1c, and visit and medication adherence, which are extracted from the data warehouse.
- Arm 3, essential to achieve Aim 2, will only occur exclusively in the primary care clinic because it requires blinding physicians to being audio recorded which is not relevant to measuring the effect of OAA on diabetes control, and would confound that measurement.
- Similar to PAM, the SEGUE and 4C analysis require RA time and effort, so will be applied to the smallest possible samples. Whereas PAM is intended to measure the effect of OAA (Arm 1) compared to control (Arm 2) on patient activation, SEGUE and 4C are intended to measure the effect of the physician knowing they are being recorded (Arm 2) versus not knowing (Arm 3) on the process (SEGUE) and content (4C) of the physician's decision making. The SEGUE checklist and the 4C coding occur while the RA is listening to the audio of a visit, randomly sampling 250 audios from the 827 primary care visit audios in Arm 2 for comparison with the 250 audios from Arm 3. Random sampling from Arm 2 primary care visits will be performed by computer without replacement and without regard to whether they are also part of the hypothesis 1A subsample.

Research activities for testing each aim: Anticipating and mitigating risks

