For the audio recording device, we plan to use VHA approved audio recorders with accompanying software, the DS-9000 and DS 9600 Olympus encrypting recorders with a pin code for security. The audios will be uploaded by the RA to a workstation desktop on to our secure VHA research server, hosted in our Center of Innovation (COIN), using the VHA approved Olympus/ODMS Dictation Module 7. Each audio file name will include the Veterans last name and date of the visit., for Arm 1), The project manager will then trim the audio to remove all the identifiers using the audacity software and upload the deidentified audio directly to the HealthPAL website(<https://va.audiohealthpal.com>) managed by the research team at the

Department of Biomedical Data Science at the Geisel School of Medicine at Dartmouth. At that point an automated script sends an email to the patient and provider (in Arm 1) providing them a link to login to access the audio from any internet enabled device. The Dartmouth system, HealthPAL,²¹ which is specifically designed for sharing audios with patients, also enables patients to selectively share their audio with others, such as family or caregivers, using a highly secure process that enables them to send an invite email and text message with a six digit code, that enables the user to set up their own unique password. This feature additionally enables the research team to track how patients are using audios including whether they are listening to them, how often, whether they share them and whether those individuals access the audios as well. Because many of the patients at participating sites are older and have low levels of technology literacy, we will make an attempt to reach by phone any subject who has not accessed HealthPAL within 7 days following their visit. These data will be variables in our analysis for the outcomes in Aim 1, e.g. for patient activation, medication adherence etc...

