As summarized in Table 4, we will apply several measures to assess the effectiveness of the intervention, testing hypotheses to achieve Aims 1 and 2. For each hypothesis, comparisons between arms will be made using mixed-effect linear or logistic regression as appropriate for the outcome, with a fixed effect of study arm, VA site, and primary vs. secondary care setting, and a random effect of provider to accommodate clustering of visits within providers. Of primary interest is the direction, magnitude, and significance of the regression coefficient associated with study arm. Primary analysis will compare arms on an intention-to-treat basis, without regard to whether audio made available in Arm 1 is actually accessed by anyone; secondary analyses will include covariates representing whether, how often, and by whom (patient or provider) audio is actually accessed in Arm 1 to assess the impact of audio use (vs. availability). As patients will be randomized to arms, we do not expect demographic or other patient differences among arms, but will conduct tests for differences, and if any variables differ significantly among arms, we will include them as covariates in the regression models.

Table 4. Hypotheses and evaluation strategy for effectiveness of intervention (Aims 1 and 2)

Hypothesis	Evaluation Strategy
1A: OAA increases patient activation.	Administer PAM (Appendix A-1) 1-2 weeks post visit via phone call and compare scores in Arm 1 vs. Arm 2
1B: OAA increases care plan adherence, including fewer no-shows and more on-time refills.	Utilizing the data warehouse measure Return Visit Adherence (RVA) and refill rates (PDC) ^{24,32,33} in Arms 1 vs. 2.
1C: OAA reduces Hgb A1c and BP	Same as above: Utilizing data warehouse measure A1c and BP.
2A: Providers obtain higher scores on measures of communication behavior when they know they are being recorded.	Completed by trained RA off of Audio: SEGUE checklist for communication completed by research team (Appendix A-2) ²⁵ , comparing randomly sampled visits in Arm 2 vs Arm 3.
2B: Providers obtain higher scores on measures of attention to patient contextual factors essential to care planning when they know they are being recorded.	4C for contextualization of care ³⁴ , comparing randomly sampled visits in Arm 2 vs Arm 3.

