As noted earlier, the PAM will be completed over the phone by the RA initially at one week after the visit (this will be extended to 10-14 days if it turns out a substantial number of patients listen to the audio more than one week after the visit).

Table 4.1 lists the calculated power for the intention-to-treat analyses for Hypotheses 1A-1C by outcome. These analyses are based on data from 1029 combined primary care and diabetes clinic visits each in Arms 1 and 2 (i.e. sample size 2058), except for measuring the effect of OAA on Hgb A1c (in 1C) which is based only on 202 diabetes clinic visits each in Arms 1 and 2 (total 404). For patient activation (1A), we assume veterans with no audio access will have a mean PAM score of 56 and standard deviation of 19.5, based on a 2016 national study of VA health care users;³⁵ clinically meaningful differences in activation have been described as 4-6 points.³⁶ Since testing hypothesis 1A requires a phone call to administer the PAM, we will randomly contact 924 participating subjects, an average of 9 calls/week across sites, which will achieve 80% power, instead of calling all 2058 subjects. Baseline rates of each undesirable outcome for 1B are derived from our previously published study in the VA using recordings without provider awareness or patient access (as in Arm 3), and we expect to find an odds ratio of 0.5 for each outcome when patients have access to audios.¹⁴ Baseline rates of each undesirable outcome for 1C are derived from the data warehouse (Chicago and Cleveland facilities – see table 3, above).

Table 4.1: Expected differences and power for planned intention-to-treat analyses for hypothesis 1A-1C

Hypothesis	Outcome	Baseline without audio available	Expected with audio available	Sample size	Power

		(Arm 2)	(Arm 1)	(total)	
1A	Patient activation (PAM 0-100 score)	56.0	60.0	924	80%
1B	Visit no-show rate	7%	4%	2058	95%
	Medication Proportion of days not covered	13%	7%	2058	80%
1C	Hgb A1c > 8 with repeat in < 6 Mo	66-70%	33-35%	404	80%
	Most Recent SBP>140 or DBP>90* with repeat in < 6 Mo	39%	24%	2058	99%

Also, while not included in Table 4.1, because it is not a primary objective of Aim 1, we will explore whether OAA is associated with fewer ED visits and hospitalizations. With the current sample size, we will in fact have 80% power to detect a decrease in inpatient admissions from 14%, the 2018 rate in our study population, to 9%.

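### On the initial schedule the PAM call and the Arm 1 reminder call both fall at about one week, so patients who listen only after the reminder can be scored before they hear the audio

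*Combined protocol and SAP*

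**What the plan says.** Hypothesis 1A compares PAM scores between Arm 1 (audio available) and Arm 2 (not available). The plan describes the timing of the PAM in two ways.

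- **A window of one to two weeks.** In Section 5.1, the notes to Figure 2 say the survey "is completed by patient 1-2 weeks after their visit", and the rationale for Figure 3 says "these calls will be spread out and administered 1-2 weeks post visit". Table 4 in Section 5.6 has "1-2 weeks post visit via phone call and compare scores in Arm 1 vs. Arm 2". The patient risk text in Section 5.1 and Section 7.0 give the same range.
- **A start at one week.** The text after Table 4 says "the PAM will be completed over the phone by the RA initially at one week after the visit". It then adds in parentheses that "this will be extended to 10-14 days if it turns out a substantial number of patients listen" later than that.

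The reminder is described under Audio recording technology in Section 5.1: "we will make an attempt to reach by phone any subject who has not accessed HealthPAL within 7 days following their visit". Only Arm 1 patients are given access to HealthPAL, so the reminder is in effect part of Arm 1.

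The primary analysis is by intention to treat on availability of the audio. The regression model has terms for arm, site, care setting and provider. Secondary analyses add covariates for actual use of the audio.

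**The concern.** The reminder can be triggered only once day 7 has passed without access. A PAM taken at one week therefore cannot reflect listening that the reminder prompts. The plan justifies the reminder by the age and limited technology skills of many patients, and those same patients are the ones a one-week PAM can miss. Blood pressure and HbA1c have a six-month window and do not share the problem.

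The extension to 10-14 days shows that the sponsor foresaw late listening, but it is incomplete. It does not say how many late listeners trigger it, when the decision is made or who makes it. It also does not say what happens to PAMs already taken at one week. Those cannot be repeated at the later time, so a switch would leave two assessment times in one outcome, with no term for timing in the model.

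The secondary audio-use analysis has a related gap. Access is not limited to access before the PAM, so a patient could count as a listener although scored beforehand.

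At stake is avoidable dilution of hypothesis 1A, for which the PAM is the only measure.

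**Working it through.** **Timeline on the initial schedule**

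1. Day 0: the visit. Arm 1 patients are emailed a link once the audio has been uploaded.
2. Day 7: an Arm 1 patient without access qualifies for the reminder.
3. About day 7: the PAM call is due in both arms. The order of the two calls and a minimum gap are not stated.
4. After day 7: listening prompted by the reminder takes place.

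If the PAM is taken at step 3, step 4 comes too late for that patient. If it is taken later in the one-to-two-week window, it may not.

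**The plan's own figure**

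Inputs from Section 5.6 and Table 4.1: means 56 and 60 (difference 4), SD 19.5, 924 subjects in total, stated power 80%. Equal arms of 462 follow from the 1:1 ratio of Arms 1 and 2. Alpha is not stated; two-sided 0.05 is assumed.

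- Required n per arm = 2 × (1.960 + 0.8416)² × 19.5² / 4² = 2 × 7.849 × 380.25 / 16 = 373.1, so 374 per arm and 748 in total.
- Standard error with 462 per arm = 19.5 × √(2/462) = 1.283.
- Power = Φ(4/1.283 − 1.960) = Φ(1.158) = 87.7%.

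The stated 80% does not reproduce; 924 is more than these inputs require. About 19% non-response (748/0.81 ≈ 924) or a design effect of 924/748 = 1.24 would reconcile the figures, but neither is stated for the PAM. The two baselines below cover both possibilities.

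**Illustration of dilution**

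Let s be the share of the 4-point effect not yet present at the PAM. The documents give no value for s; 10%, 20% and 30% are assumptions. The difference becomes 4 × (1 − s), and power is Φ(difference/SE − 1.960). The standard error is 1.283 for 462 per arm, and 19.5 × √(2/374) = 1.426 for 374 per arm, the size at which the stated 80% would be right.

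| s | Difference | Power, 462 per arm, all complete | Power, effective 374 per arm |
|---|---|---|---|
| 0 | 4.0 | 87.7% | 80.1% |
| 10% | 3.6 | 80.1% | 71.4% |
| 20% | 3.2 | 70.3% | 61.2% |
| 30% | 2.8 | 58.8% | 50.1% |

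With 462 per arm, the difference detectable with 80% power is 2.8016 × 1.283 = 3.59 points. About 10% of the effect can then be lost before power falls below 80%. If the extra subjects are needed for non-response or clustering, there is no such margin.

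**The case against.** Several points on the other side stand.

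- **The timing is a risk, not a certainty.** A reader might infer that prompted listeners are always scored before they hear the audio. The documents do not support this: most statements of the window allow one to two weeks, the calls are to be spread out, and the one-week rule is only the initial one. Patients who listen in the first week are unaffected.
- **The plan has a fallback.** If 20% or 30% of the effect were being lost to late listening, the extension would probably be triggered. The lower power figures apply only if every PAM stayed early.
- **The primary contrast is valid.** The plan states: "Primary analysis will compare arms on an intention-to-treat basis, without regard to whether audio made available in Arm 1 is actually accessed by anyone". A one-week PAM validly estimates the effect of availability at one week. It may, however, miss the effect of Arm 1 as planned, reminder included.
- **A switch need not bias the comparison.** A reader might infer that a data-driven change of window confounds timing with arm. Nothing limits the extension to one arm, and its trigger is audio access, not PAM scores. Applied to both arms together, it averages two assessment times. That blurs what is estimated, but does not by itself favour an arm.
- **The size is assumed.** The table supposes that the whole 4-point effect comes through listening and is absent in those who have not yet listened. The documents state neither.
- **Other rules may exist.** Section 6.0 mentions a Data Analysis Plan approved by the DSMB. It is not among the documents reviewed and may define the trigger.

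None of this sets the order of the two calls or settles what happens to PAMs already taken at one week.

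**Conclusion.** The point holds as a low-cost improvement. On the initial schedule the PAM and the reminder coincide, and prompted listeners can be scored too early. The extension that would address this is conditional and undefined. Any effect on hypothesis 1A is towards zero, and its size cannot be derived from the documents.

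The fall from 88% to 80%, 70% or 59% power is illustration only. It rests on two-sided 0.05, 462 completers per arm, no allowance for clustering, and assumed losses of 10%, 20% or 30% of the 4-point effect. If the plan's 80% already allows for non-response or clustering, the same losses give 71%, 61% or 50%.

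The failure of 80% at 924 to reproduce is a separate matter. It errs towards more power and neither supports nor weakens the point about timing.

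**What to change.** 1. In Section 5.6, set the PAM at 10-14 days after the visit in both arms from the first patient, and delete the conditional extension.
2. Align the one-to-two-week wording in Section 5.1 (notes to Figure 2, rationale for Figure 3, patient risk text), Table 4 and Section 7.0.
3. Under Audio recording technology, require the reminder attempt soon after day 7 and before the PAM call. An attempt on day 8, for example, leaves two to six days to listen.
4. In the secondary audio-use analysis of PAM, count only access time-stamped before the PAM. The platform already records when audio is accessed.

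The cost is wording and call scheduling. The number of calls is unchanged, and the window lies inside the one to two weeks already described to patients.

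There are three downsides. The delay is slightly longer. A few more patients may be unreachable. Arm 1 patients who have not opened the audio receive a staff contact before a self-reported outcome, which Arm 2 patients do not; that contact is already part of the intervention as planned, but should be acknowledged when the result is interpreted. Patients reached late by the reminder, or who listen after the PAM, will still be scored early, so the change reduces the problem without removing it.

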Table 4.2 lists the calculated power for the analyses for Hypothesis 2A and 2B (comparisons of Arm 2 vs. Arm 3) based on actual Veteran visits by outcome. Baseline SEGUE scores are based on SEGUE's validation study among general internists (mean 17.5, sd 1.77); that study found that medical students in a skills lab achieved mean SEGUE scores of 21.1 (sd 2.1), and we take that as our minimal expected level of improvement from knowledge that one is being observed. Baseline rates of contextual probing and planning are based on our prior study in the VA using recordings without provider awareness or patient access (as in Arm 3), and incorporate the expectation that contextual red flags suitable for probing will be present in 2/3 of encounters and contextual factors that should be incorporated in planning will be present in 1/4 of encounters overall.¹⁴ Expected increases in probing and planning are based on odds ratios from our prior study comparing these measures in undercover visits to providers with the same cases presented to medical students in a testing setting (and are thus conservative measures of how much better providers would likely perform if they were aware vs. unaware they were being tested).¹³ To obtain at least 80% power for each of these comparisons, we will randomly sample 250 primary care clinic visits (from 827 Arm 2 primary care visits), and enroll all 250 primary care visits in Arm 3 for the SEGUE and 4C coding processes. For 4C, we expect 168 visits/arm with red flags suitable for probing and 63 visits/arm with contextual factors suitable for planning.

Table 4.2: Expected differences and power for planned analyses for hypotheses 2A and 2B

Outcome	Baseline (doctor unaware, n=250)	Expected (doctor aware, n=250)	Sample size (total)	Power
SEGUE provider score	17.5	21	500	99%
Contextual probing rate ^{13,26}	32%	47%	500	80%
Contextual	59%	82%	500	82%

planning rate ^{13,26}				
--------------------------------	--	--	--	--

All effects measured in Aim 1 and 2 will be adjusted for patient sociodemographic characteristics which will be obtained from the CDW (including age, gender, and race) or from administering the REALM-SF to assess literacy. Internet access, for those in the intervention arm, will be ascertained by census track using geocoding of patient addresses, based on FCC data, a method developed by Perzynski et al.^{37,38}

Aim 3:

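### Table 4.1: the 80% power entries for A1c and for days not covered do not follow from their printed rates and sample sizes

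*Combined protocol and SAP*

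**What the plan says.** In section 5.6, the text introducing Table 4.1 reads "Table 4.1 lists the calculated power for the intention-to-treat analyses for Hypotheses 1A-1C by outcome". The 1B and blood pressure rows use 1029 visits per arm (2058 in total). A1c is the exception, "which is based only on 202 diabetes clinic visits each in Arms 1 and 2 (total 404").

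The rows at issue, as printed (Arm 2 vs Arm 1):

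- "Visit no-show rate": 7% vs 4%, N=2058, power 95%.
- "Medication Proportion of days not covered": 13% vs 7%, N=2058, power 80%.
- A1c above 8 with a repeat inside six months: 66-70% vs 33-35%, N=404, power 80%.

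For the two 1B outcomes the text gives the effect: "we expect to find an odds ratio of 0.5 for each outcome when patients have access to audios". No odds ratio is stated for A1c. The section gives no alpha, sidedness, intraclass correlation, design effect or attrition rate for these figures, although the planned models carry a random effect for provider.

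For the 4C outcomes in Table 4.2 the text does give the evaluable numbers: "For 4C, we expect 168 visits/arm with red flags suitable for probing and 63 visits/arm with contextual factors suitable for planning".

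**The concern.** A power column should be recoverable from the rates and N beside it. Halving a rate near two thirds with 202 patients per arm is a very large effect, and 80% looks far too low for it. Thirteen against seven per cent with more than 1000 per arm also looks too strong for 80%. The ordering of the two 1B rows is wrong on its face: with equal N and a common odds ratio, a 13% baseline carries more information than a 7% baseline, so its power cannot be lower.

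What is at stake is interpretation, not trial size. Section 5.6 says that the sample sizes were derived from these power calculations. As the table stands, a reader cannot tell which effect, or which number of evaluable patients, the 80% for A1c and for days not covered belongs to.

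**Working it through.** **Formula.** For two proportions with n per arm, p̄ the mean of p1 and p2, and z = 1.96 (two-sided 5%, assumed):

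power = Φ{ [|p1 − p2| − z·√(2p̄(1 − p̄)/n)] / √([p1(1 − p1) + p2(1 − p2)]/n) }

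**Step 1: calibrate on the plan's own figures (Table 4.2, with the per-arm numbers from the text).**

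- Contextual probing, 32% vs 47%, n=168: (0.15 − 1.96 × 0.0533)/0.0527 = 0.86, power 80.6% (stated 80%).
- Contextual planning, 59% vs 82%, n=63: (0.23 − 1.96 × 0.0813)/0.0786 = 0.90, power 81.6% (stated 82%).
- A one-sided 5% test would give 88.1% and 89.0%, which does not match.

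Two-sided 5% with no design effect is therefore the basis that fits.

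**Step 2: apply it to Table 4.1.**

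| Row | Inputs | n per arm | Computed | Stated |
|---|---|---|---|---|
| A1c | 66% vs 33% | 202 | >99.9% | 80% |
| A1c | 70% vs 35% | 202 | >99.9% | 80% |
| A1c, 66% of 202 evaluable | 66% vs 33% | 133 | 99.99% | 80% |
| A1c, same, smallest printed gap | 66% vs 35% | 133 | 99.94% | 80% |
| Days not covered | 13% vs 7% | 1029 | 99.5% | 80% |
| Days not covered, worst rounding | 12.5% vs 7.5% | 1029 | 96.6% | 80% |
| No-show, as printed | 7% vs 4% | 1029 | 84.8% | 95% |
| No-show, odds ratio 0.5 | 7% vs 3.63% | 1029 | 92.7% | 95% |
| No-show, simple halving | 7% vs 3.5% | 1029 | 94.6% | 95% |

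Worked line for days not covered: (0.06 − 1.96 × 0.01323)/0.01316 = 2.59, and Φ(2.59) = 0.995. On the printed rates, 80% power would need about 392 per arm for days not covered and about 31-35 per arm for A1c.

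The odds ratio of 0.5 gives 0.5 × 0.07/0.93 = 0.0376 in odds, or 3.63%, for no-show, and 6.95% for days not covered. Both agree with the printed 4% and 7% after rounding.

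**Step 3: could days not covered be a continuous analysis?** The plan allows linear models. Power of 80% for a mean difference of 0.06 needs SD = 0.06/(2.80 × √(2/1029)) = 0.49. A variable confined to 0-1 with mean 0.13 has SD of at most √(0.13 × 0.87) = 0.34, and with mean 0.07 at most √(0.07 × 0.93) = 0.26. Even at those maxima power is 99.5%, and any smaller SD raises it.

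**Step 4: could one alpha or one design effect explain the column?**

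- Alpha: days not covered would need about 0.0002 and A1c below 0.00000001 to fall to 80%. No-show as printed would need about 0.18 to reach 95%.
- Design effect: 2.6 brings days not covered to 80%, but leaves A1c at about 99% and cuts no-show as printed to 46%.

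No common value fits.

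**Step 5: a possible origin of the A1c 80% (conjecture).** Apply an odds ratio of 0.5 instead of a halved rate: 66% becomes 49.3% and 70% becomes 53.8%. Restrict to the 66-70% who have a qualifying A1c and a repeat: 0.66 × 202 = 133 and 0.70 × 202 = 141 per arm. Power is then 79.3% and 80.1%.

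**The case against.** **The N column may not be the N behind the power.** Table 4.2 prints 500 for both 4C rows, yet their power follows from 168 and 63 per arm. If Table 4.1 follows the same habit, the A1c power could be right and the printed effect or N wrong, as in Step 5. This stands in part. It does not rescue the row, because 133 per arm with the printed rates still gives more than 99.9%, and the plan states an odds ratio of 0.5 only for the 1B outcomes. It does mean that overwriting the cell with a figure above 99.9% could introduce a new error.

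**Clustering by provider could lower true power.** It could, but no intraclass correlation or design effect is given. Reaching 80% would need about 2.6 for days not covered and 5.8 to 6.5 for A1c. Different unstated inflations for each row are not a calculation that a reader can follow.

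**No-show.** A reader might infer that this row overstates power by ten points and hides the thinnest margin in the table. The documents do not support that. The 85% depends on taking 4% literally. The plan's own odds ratio gives about 93%, and halving to 3.5%, which also prints as 4%, gives about 95%. At 3.63%, 80% power needs 693 of the 1029 per arm, so the margin is not thin.

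**PAM and admissions.** A reader might also add these to the list. For PAM the text says "we will randomly contact 924 participating subjects", and the stated 80% fits about 748 completers among them (88% if all 924 complete). For the exploratory admissions figure, 14% vs 9% computes to 94.5%, but rounding (13.5% vs 9.5%) reaches 81.2%. Neither is an established error.

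**Direction.** Both clear mismatches understate power, which is the safe direction. That is true, and it limits the consequence.

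**Conclusion.** Two entries are wrong as written. On the printed inputs, A1c power is above 99.9% and days-not-covered power is 99.5% (96.6% at the least favourable rounding), each against a stated 80%. No rounding, continuous analysis, common alpha or common design effect repairs them. The ordering of days not covered (80%) below no-show (95%), at the same N and odds ratio, is an internal contradiction on any common alpha and design effect.

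The exact figures rest on a two-sided 5% test with independent visits. The plan does not state this; it is inferred from the 4C rows of Table 4.2.

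No-show is a lesser point: the rounded rate does not regenerate its power, and the unrounded one nearly does. The blood pressure entry is not in question. It would be wrong to infer that the trial is too small, since on the printed inputs every outcome in Table 4.1 reaches the plan's 80% target.

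**What to change.** Recompute the three rows and state, for each, alpha, sidedness, any design effect and the evaluable N.

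- **Days not covered:** print power above 99% on the current inputs, or print the inputs that give 80%. Say whether the outcome is analysed as binary or continuous.
- **A1c:** first reconcile the intended effect and the evaluable N. Then print either those inputs with 80%, or the current inputs with above 99.9%. Do not change the power cell alone.
- **No-show:** print the unrounded expected rate with its matching power: 3.6% with about 93%, or 3.5% with about 95%. The first agrees with the stated odds ratio.

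The cost is a correction to one table and its accompanying text. Sample size, design and analysis are unchanged.
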